9. PHARMACODYNAMIC ASSESSMENTS

PD assessment time points are given in the Schedule of Events ([Table 1](#)).

Patients will also be asked to take part in an optional one-to-one guided interview after their dose to discuss their dosing experience in their own words to gather qualitative information.

Patients will self-complete the PD assessments using the Electronic Patient Reported Outcome system (ePRO) system, unless otherwise indicated.

9.1. Stanford Expectation of Treatment Scale

As a patient's response to treatment may be influenced by the expectations that the patient has before initiating treatment, the influence of participant expectancy may reduce statistical power in a clinical study. The Stanford Expectations of Treatment Scale (SETS) (Younger, 2012) is a 6-item scale for measuring positive and negative treatment expectancies. SETS is used to improve statistical sensitivity for detecting treatment differences in clinical studies. The SETS will be administered prior to the first psychedelic preparation session on Day -7.

9.2. Mystical Experience Questionnaire

The extent of a patient's mystical experience after receiving BPL-003 will be assessed using the Mystical Experience Questionnaire (MEQ30) that was developed and validated through factor analysis of retrospective accounts of experiences with psilocybin-containing mushrooms ([Maclean, 2012](#)). That analysis provided a 4-factor structure of the MEQ30: mystical, positive mood, transcendence of time and space, and ineffability. The questionnaire comprises a list of 30 phenomena. Patients will rate the degree to which they experienced each phenomenon using the following scale:

- 0 = none; not at all
- 1 = so slight cannot decide
- 2 = slight
- 3 = moderate
- 4 = strong (equivalent in degree to any other strong experience)
- 5 = extreme (more than any other time in my life and stronger than 4)

9.3. Ego Dissolution Inventory

The extent of a patient's dissolution of ego after receiving BPL-003 will be assessed using the EDI ([Nour, 2016](#)).

The inventory comprises 8 statements. Patients will rate their agreement with each statement by marking on a visual analogue scale (VAS) from 0 ("No, not more than usually") to 100 ("Yes, entirely or completely").

9.4. 5-Level EuroQol 5-Dimension

The 5-level EQ-5D version (EQ-5D-5L) consists of 2 parts: the EQ-5D descriptive system and the EQ-VAS.

The EQ-5D-5L is a self-assessed, health-related quality of life questionnaire. The scale measures quality of life on a 5-component scale, including mobility, self-care, usual activities, pain/discomfort, and anxiety/depression. Each level is rated on a scale that describes the degree of problems in that area (eg, I have no problems walking about, slight problems, moderate problems, severe problems, or unable to walk). This tool also has an overall health scale (EQ-VAS), where the rater selects a number between 1 and 100 to describe the condition of their health, 100 being the best imaginable. Convergent validity was demonstrated by a correlation between EQ-5D-5L and the dimensions of WHO-5 ($r=0.43$, $p<0.001$) (Janssen, 2013). The EuroQol approach is reliable, with average test-retest reliability using interclass coefficients with mean of 0.78 and 0.73 (Brooks, 1996).

9.5. Timeline Follow-Back

The alcohol Timeline Follow-Back (TLFB; calendar prompt interview) originally developed by Sobell and Sobell (Sobell, 1992) was adapted from the Form 90 structured interview (Miller, 1996) to indicate “active” recording of each day in the recall period (i.e., “abstinent” or “alcohol consumed”) with standard and high-strength beverage types typically consumed by the study clinical population before treatment to assist the interviewer record units consumed on a drinking day from the participant’s verbatim report.

The TLFB has been shown to have good psychometric characteristics with a variety of drinker groups, and it can generate variables that provide a wide range of information about an individual’s drinking (e.g., pattern, variability, and magnitude of drinking). The method is recommended for use when relatively precise estimates of drinking are necessary, especially when a complete picture of drinking days (i.e., high- and low-risk days) is needed. Although TLFB summary data have been found to be generally reliable, as with all drinking assessment methods, exact day-by-day precision cannot be assumed or necessarily expected. Overall, the TLFB method provides a relatively accurate portrayal of drinking and has both clinical and research utility.

9.6. Qualitative Interview

After dosing, patients will be asked to take part in an optional qualitative interview. If they agree, they will have a one-to-one guided interview with independent researchers trained in microphenomenology methods to discuss their psychedelic experience. This will be done either face to face at the clinic or via video call. The qualitative interview will provide a more nuanced understanding of the phenomenology of BPL-003 effects compared with the questionnaires used in this study. Data from this interview will help inform future clinical studies of this compound.

The interview will

- Provide a holistic phenomenological description of the experience during the entire drug session
- Identify, within the holistic description, one or more phases or moments of interest, e.g., peak or mystical experience (if present), experience of ego dissolution, or otherwise salient aspects of the experience
- Outline the general structure of BPL-003 experience and identify unique and common features between individual experiences

- Characterise, describe, or determine potential therapeutic mechanisms, effects, and processes resulting from the BPL-003 experience
- Identify possible risks and their mitigation

Details of the methodology and interview structure to be used can be found in the Qualitative Interview Study Manual.

9.7. Optional Semi-Structured Interview & Psychological Change Measures

The optional semi-structured interviews will take place on Days 1 and 84. These interviews will be topic-guided, audio-recorded, qualitative interviews to understand a patient's psychological changes from shortly after dosing (Day 1) until Day 84.

Patients will be invited to complete an optional online psychological change questionnaire on Days -3, 1, 28, and 84. The questionnaire will consist of validated scales measuring psychological changes such as personality traits, anxiety traits and avoidance, beliefs about self, others and environment, suggestibility, absorption, expectations about the treatment, and wellbeing and resilience pre- and postdosing, to understand the potential effect of BPL-003 dosing combined with relapse prevention psychotherapy.

Details of the methodology, interview structure and psychological changes measures can be found in the Psychological Change Study Manual.

9.8. Montgomery–Asberg Depression Rating Scale

The Montgomery–Åsberg Depression Rating Scale (MADRS) will be completed at the visits outlined in [Table 1](#).

Via the electronic Clinical Outcome Assessment (eCOA), an appropriately trained member of the study team will use the Structured Interview Guide for the MADRS (SIGMA) to interview the subject moving from broad questions about symptoms to more detailed ones which allow the precise rating of symptom severity. The MADRS is a 10-item diagnostic questionnaire used to measure the severity of depressive episodes in patients with mood disorders (Williams, 2008). A higher MADRS score indicates more severe depression, and each item yields a score of 0 to 6. The overall score ranges from 0 to 60. The questionnaire includes questions on the following symptoms: (1) apparent sadness, (2) reported sadness, (3) inner tension, (4) reduced sleep, (5) reduced appetite, (6) concentration difficulties, (7) lassitude, (8) inability to feel, (9) pessimistic thoughts, and (10) suicidal thoughts. The usual cutoff points are:

- 0 to 6 = normal/symptom absent
- 7 to 19 = mild depression
- 20 to 34 = moderate depression
- >34 = severe depression.

9.9. Alcohol Craving Questionnaire

The Alcohol Craving Questionnaire Short Form Revised (ACQ-SF-R) ([Singleton, 1997](#)) will be completed at Baseline (pre-dose on Day 0) and at the visits on Days 1, 7, 28, 56, and 84.

9.10. Craving Visual Analogue Scale

A Craving VAS will be used on dosing day to assess the relative craving status of the patient before discharge on Day 0 dosing compared to prior to dosing. The scale will be completed on admission (A) and again at the point of discharge (B). If the rating at B is greater than at A, then an additional craving talk down procedure will be implemented and VAS B repeated. Patients will be discharged only when their VAS rating at B is the same or lower than at A.

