13. Patients will be asked to take part in an optional qualitative interview. If they agree, the interview will commence on cessation of the psychedelic experience and before any postdose questionnaires are completed. The therapist will remain with the patient until the cessation of the psychedelic experience.
14. This can be either face to face or remote.
15. AUD relapse prevention psychotherapy (see [Appendix 4](#)) will begin during Psychedelic Preparation sessions.
16. Patients will fast (no food or drink, except water) for at least 8 hours before blood draws at the Screening visit

17. Only section I (AUD section) of the MINI to be completed at Day 84.
18. The PK blood sample will be taken three times after dosing at 5, 15 and 60 minutes post dose (+5 minutes for all timepoints) Details concerning the blood draw are provided in the Study Manual.
19. Craving VAS scale to be completed on admission and before discharge on dosing (Day 0). If greater at discharge than admission, then talk down and repeat scale and repeat until no higher than admission before discharging.
20. SETS will be administered prior to beginning the first psychedelic preparation session.
21. On Day 0 the C-SSRS will be done as part of discharge safety check at the end of Day 0.
22. Therapists may complete the Treatment Model feedback questions once from Day 15 to Day 42.
23. Cardiac Telemetry will be performed on Day 0 starting approximately 30 minutes before dosing up to 90 minutes post dose and any anomalies reported
24. CDT to be assessed in blood sample.

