3.3. Exploratory Endpoints

Pharmacokinetic:

- Blood samples to determine 5-MeO-DMT and its metabolites (including bufotenine) plasma concentrations will be taken after dosing on Day 0.

Drinking Craving:

- Change in alcohol craving as measured by Alcohol Craving Questionnaire (ACQ) at Days 1, 7, 28, 56, and 84 compared to Baseline (pre-dose on Day 0)
- Alcohol cravings as measured by Craving Visual Analogue Scale (VAS)
- Alcohol withdrawal symptoms as measured by Clinical Institute Withdrawal Assessment (CIWA-Ar)
- Consequences of alcohol use as measured by Short Inventory of Problems (SIP)

Alcohol Use:

Using the Timeline Follow-Back (TLFB) interview, the following parameters of alcohol use in the 90 days before dosing and endpoint will be recorded:

- Percentage of Heavy Drinking Days (PHDD) in 85d prior D-3 (or start of detox) vs PHDD post-dosing measured on d14, d28, d56, d84.
- Percentage of drinking days (PDD) in 85d prior D-3 (or start of detox) vs PDD post-dosing measured on d14, d28, d56, d84.
- Mean Units per day (UPD): In 85d prior D-3 (or start of detox) vs UPD post-dosing measured on d14, d28, d56, d84.
- Abstinence: Percentage of Abstinent days (PAD) in 85d prior D-3 (or start of detox) vs PAD on d14, d28, d56, d84 (with biomarker verification).
- Longest duration (days) of continuous abstinence
- Number of days after BPL-003 dosing to first drink
- Number of days after BPL-003 dosing to first HDD (defined by UK government as >7 units a day for a woman and >9 units per day for a man)
- Average number of standard units of alcohol consumed per week in 85d prior D-3 (or start of detox) vs post-dosing measured on d14, d28, d56, d84 (and reported referencing UK risk levels)
- Maximum number of standard units of alcohol consumed on any one day

Correlation of PD effects with alcohol use and related symptoms

The correlation of the occurrence of a “complete mystical experience” and “ego dissolution”, measured by the MEQ30 and EDI, with improvement in alcohol use and craving (measured by AQC, TLFB, EtG, CDT)

Biomarkers

- Alcohol use as measured by EtG in urine at Days 1, 28, 56, 84 compared to Screening
- Alcohol use as measured by CDT in blood at Days 28 & 84 compared to Screening

Wellbeing

- Change in Montgomery–Asberg Depression Rating Scale (MADRS) at Days 28, 56, and 84 compared to Baseline
- Change in Clinical Global Impression Severity (CGIS) at Days 1, 28, 56, and 84 compared to Baseline

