14.2.9	Summary of Craving Visual Analogue Scale (VAS)	ITT	16.2.6.9	T_PD1
14.2.10	Summary of Clinical Global Impression of Severity (CGI-S)	ITT	16.2.6.10	T_PD6
14.2.11	Summary of Patient Global Impression of Change (PGIC)	ITT	16.2.6.11	T_PD6
14.2.12	Summary of Clinical Institute Withdrawal Assessment for Alcohol-Revised (CIWA-Ar)	ITT	16.2.6.12	T_PD1
14.2.13	Summary of Short Inventory of Problems (SIP)	ITT	16.2.6.13	T_PD2
14.3	SAFETY DATA			
14.3.1.1	Overall summary of treatment-emergent adverse events	Safety	16.2.7.1	T_AE2
14.3.1.2	Summary of treatment-emergent adverse events	Safety	16.2.7.1	T_AE1
14.3.1.3	Summary of drug-related treatment-emergent adverse events	Safety	16.2.7.1	T_AE1
14.3.1.4	Summary of treatment-emergent adverse events by maximum severity	Safety	16.2.7.1	T_AE3
14.3.1.5	Summary of treatment-emergent adverse events by day of onset	Safety	16.2.7.1	T_AE4
14.3.2.1	Listing of fatal adverse events	Safety	16.2.7.1	L_AE1_PG
14.3.2.2	Listing of non-fatal serious adverse events	Safety	16.2.7.1	L_AE1_PG
14.3.2.3	Listing of other significant adverse events	Safety	16.2.7.1	L_AE1_PG
14.3.3	Narratives of deaths, other serious and significant adverse events	Safety		-
14.3.4.1	Summary of post dose clinically significant abnormal laboratory values by treatment and planned relative time	Safety	16.2.8.1, 16.2.8.3, 16.2.8.5	T_LB4
14.3.4.2	Summary of post dose clinically significant abnormal alcohol biomarker values by treatment and planned relative time	Safety	16.2.8.7	T_LB4
14.3.5.1	Summary of chemistry laboratory values	Safety	16.4	T_LB2
14.3.5.2	Summary of haematology laboratory values	Safety	16.4	T_LB2
14.3.5.3	Summary of coagulation laboratory values	Safety	16.4	T_LB2
14.3.5.4	Summary of alcohol biomarker data	Safety	16.4	T_LB2

Table	Description	Population	Source Listing	Template (Shells below)
14.3.6.1	Summary of vital signs	Safety	16.4	T_VS1
14.3.6.2	Summary of vital signs of potential clinical importance by treatment, planned relative time and parameter	Safety	16.2.9.1	T_VS2
14.3.6.3	Summary of vital signs of potential clinical importance by parameter and treatment (excluding baseline time point)	Safety	16.2.9.1	T_VS3
14.3.6.4	Summary of post dose clinically significant vital signs	Safety	16.2.9.2	T_VS4
14.3.6.5	Summary of peak vital signs ranges by treatment, ranges and parameter – Day 0 post dose	Safety	16.2.9.3	T_VS5
14.3.6.6	Summary of peak vital signs by treatment and parameter - baseline and day 0 post dose	Safety	16.2.9.3	T_VS6

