6.2 Analysis and reporting

Patient will rate their desire to alcohol in a 100 mm line where 0=Not at all and 100=Extremely high. The length in mm will indicate a patients desire for alcohol.

7 Clinical Institute Withdrawal Assessment for Alcohol-revised (CIWA-Ar)

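### The SAP does not say which discharge craving VAS rating is summarised; if it is the last one, after talk-down, no patient discharged under the rule can show an increase

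*Protocol*

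**What the plan says.** Protocol 9.10 gives the purpose of the measure: "A Craving VAS will be used on dosing day to assess the relative craving status of the patient before discharge on Day 0 dosing compared" with the state before dosing. It is rated on admission (A) and again at the point of discharge (B). The rule for a high B is: "If the rating at B is greater than at A, then an additional craving talk down procedure will be implemented and VAS B repeated". The condition for leaving is: "Patients will be discharged only when their VAS rating at B is the same or lower than at A". Footnote 19 to Table 1 agrees and sets no limit on the number of repeats: "If greater at discharge than admission, then talk down and repeat scale and repeat until no higher than admission before discharging".

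Protocol 3.3 and SAP 4.2.3 list the VAS as an exploratory endpoint. SAP Table 14.2.9 summarises it in the ITT population by planned time, using template T_PD1. The scoring text in SAP Appendix A 6.2 is two sentences: "Patient will rate their desire to alcohol in a 100 mm line where 0=Not at all and 100=Extremely high", and "The length in mm will indicate a patients desire for alcohol". Neither document says which B is the analysis value, whether every B is kept, or whether talk-downs are counted.

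**The concern.** One number serves as both a discharge check and an endpoint. The check works in one direction only: a B above A is followed by talk-down and rated again, while a B at or below A stands. Upward variation is therefore removed and downward variation is kept. Talk-down is also a non-drug intervention aimed at the quantity being measured.

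If the last B is summarised, part of any fall comes from the rule and part from the talk-down, and both would be read as following BPL-003. There is no control arm (Protocol 6.5), so nothing in the study could separate them. The VAS is also the only craving measure after dosing on Day 0. The ACQ is taken before dosing that day and next on Day 1 (Protocol 9.9), and the discharge questionnaire in Protocol Appendix 2 has no craving item. If first ratings and talk-downs go unreported, a rise in craving between dosing and discharge would appear in no summary table.

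**Working it through.** The plan gives no figure for the VAS, so there is none to reproduce. The question is what happens if the last B is analysed.

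**Inputs from the documents.** B is repeated only when B > A; final B ≤ A (Protocol 9.10, Table 1 footnote 19); scale 0 to 100 mm (SAP Appendix A 6.2); up to 12 patients, one arm (SAP 5, Protocol 6.5).

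**Assumed, not in the documents.** The SD, s, of the difference D = first B − A: 10, 15 or 20 mm, with D normal.

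**Step 1: the constraint.** For every patient discharged under the rule, final B − A ≤ 0. The share who can show an increase is 0%, and the mean change is zero or negative. This needs no assumption about s.

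**Step 2: smallest size with no true change.** The mildest outcome the rule allows is that a high B falls just to A, so that the recorded change is min(D, 0). For D ~ N(0, s²):

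E[min(D, 0)] = −s·φ(0) = −0.399 s

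- s = 10: −4.0 mm
- s = 15: −6.0 mm
- s = 20: −8.0 mm

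It is larger if talk-down takes ratings below A.

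**Step 3: a true rise.** For D ~ N(δ, s²), E[min(D, 0)] = δ − [δ·Φ(δ/s) + s·φ(δ/s)]. With δ = +s this is s·[1 − (0.841 + 0.242)] = −0.083 s. At s = 15 mm, a true mean rise of 15 mm would be recorded as a fall of about 1.2 mm. With δ = −s the recorded mean is −1.083 s, so the distortion is only 0.083 s when craving truly falls that much.

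**Step 4: simulation on the bounded scale.** 20,000 trials of 12 patients, no true change, assumed mean craving 30 or 50 mm, between-patient SD 20 mm, and independent noise on each rating. In the mildest version final B = min(first B, A). In the redraw version B is drawn again until it is ≤ A.

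| Noise SD per rating | First B, mean change | Last B, mildest | Last B, redraw |
|---|---|---|---|
| 5 mm | −0.01 to +0.02 | −2.7 to −2.8 | −4.2 to −4.4 |
| 10 mm | −0.06 to +0.06 | −5.3 to −5.5 | −8.1 to −8.8 |
| 15 mm | +0.01 to +0.05 | −7.6 to −8.2 | −11.6 to −12.9 |

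On the first B, 48 to 50% of patients show an increase; on the last B, none do. A 95% interval for the mean change lies wholly below zero in 2 to 3% of trials on the first B (nominal 2.5%), in 60 to 63% on the last B in the mildest version, and in over 99% in the redraw version.

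**Step 5: how often the rule would act.** If each patient has a 50% chance of B > A, the chance of at least one talk-down in 12 is 1 − 0.5¹² = 0.9998. If ties or a true fall cut that to 10%, it is 1 − 0.9¹² = 0.72.

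**The case against.** The strongest reply is that the plan may already lead to the right value. SAP 12.1 leaves data from unscheduled time points out of summaries and puts them in listings. Only two VAS ratings are planned, so a repeat after talk-down could count as unscheduled. SAP 12.2 and Protocol 11.6 also summarise the out-of-range value, not its repeat, for laboratory tests repeated after baseline. Both lean towards the first B. Neither settles it: a repeat B is required by the protocol and taken at the scheduled discharge point, the SAP does not call it unscheduled, and the laboratory rule covers laboratory tests only. A programmer could reasonably take the last B as the discharge value.

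Several limits stand in full:

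- Template T_PD1 has no change-from-baseline columns, and the VAS endpoint, unlike the ACQ endpoint, is not worded as a change. SAP 16 does say in general that questionnaire changes will be summarised. Without change columns, the discharge mean is still held at or below the admission mean.
- The interval results in the working are illustrative, since T_PD1 shows no intervals.
- Listing 16.2.6.9 has date, time and comment columns, and complete listings are planned. With at most 12 patients, retained repeats would be visible there.
- All millimetre figures rest on an assumed SD.

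A reader might infer that the planned table is biased as it stands, that the change must come out negative, or that the plan conceals a safety signal. The documents do not support these. The bias arises only if a repeated B is summarised. The rule forces a change of zero or below, not strictly below. Craving is not among the safety endpoints, and nothing says that first ratings are discarded.

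**Conclusion.** The one-way rule is certain from the protocol text, and so is the gap: no text identifies the B that Table 14.2.9 summarises. If it is the last B, no patient discharged under the rule can show an increase, and the discharge mean cannot exceed the admission mean even with no drug effect. The apparent fall is then at least about 0.4 SD of the A-to-B difference. That size assumes no true change and normal differences, with an SD that the documents do not give; the direction depends on neither the SD nor normality. If the first B is used, or if no patient's first B exceeds A, there is no bias.

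The consequence is limited. This is one exploratory, descriptive Day 0 measure in a study that tests no hypotheses, and the ACQ, which carries the change-in-craving endpoint to Day 84, has no such rule. The point still merits correction, because a table produced in line with the plan could show an artefact that nothing in a single-arm study would reveal.

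**What to change.** In SAP Appendix A 6.2, state that the discharge value for analysis is the first B rating, taken before any talk-down, and footnote Table 14.2.9 accordingly. Add to that table the number and percentage of patients who needed talk-down and the number of repeat ratings. Show every repeat with its time in Listing 16.2.6.9 and leave repeats out of the summary. The discharge procedure itself is not touched.

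The cost is one SAP sentence, one footnote and one count. The first rating is already taken under the protocol, so no new assessment is needed. Before database lock, confirm that the eCRF keeps the first B when a repeat is entered. If it holds only one B per patient, the table should say that the value may follow talk-down and should not be read as a change in craving after BPL-003.
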